2. Attach electrodes (so they're visible in the baseline video for optimal blinding).
3. Check resistance through electrodes. If $< 100 \Omega$, look for a short and correct it. If resistance remains out of range, do not proceed without specific approval from PI. Record resistance.
4. Optional but recommended bathroom stop
5. Procedures below are performed in a quiet room with only participant and study staff present but not conversing
6. All videos are recorded from the elbows up for later blinded ratings of tics
7. 5-min video-recorded baseline session, also rated live at the first visit to record baseline tic

frequency

8. At this point, the PI or designate will review the inclusion and exclusion criteria (including mean baseline tic frequency $\geq 1/\text{min.}$) and document eligibility for the study before additional procedures
9. Determine stimulation threshold for a train of 8 pulses (12 Hz, pulse width 200 μs), starting at 1mA and increasing until a twitch of the thumb is seen, to a maximum of 20mA (expected range 2-15 mA, *personal communication, [name] to [name]*). Some subjects may wish to withdraw at this point if suprathreshold stimulation is too uncomfortable, but in the Nottingham report, participants age 15 and up found the stimulation tolerable. Since electrode placement can change slightly between visits, on the second visit the threshold is verified and adjusted as needed. We record the threshold at each visit.
10. Resume video recording
11. Synchronize clocks for video, urge rating software, and stimulation
12. MNS stimulation on or off blocks as follows, without planned breaks (total 29-44 min.)
 - a. Two 1-min. blocks of MNS on and two 1-min. sessions off, the order of these 4 sessions randomized (*this design matches the Nottingham study*)
 - b. 5-min. block MNS off
 - c. 5-min. block MNS on
 - d. 5-min. block MNS off
 - e. 5-min. block MNS on
 - f. 5-minute stimulation **off** blocks until tics return to baseline frequency (min. 1 block, max. 4 blocks)
13. Stop video recording
14. CGI-I (Clinical Global Impression of Improvement) rating for tics by participant and investigator
15. Debrief
 - a. ratings of tic improvement and discomfort using the CGI Efficacy Index
 - b. ask for comments on benefit, tolerability, side effects
 - c. participant and staff guess whether this was active or control stimulation day (*to test adequacy of blinding*)
 - d. ask if they think they would use a portable stimulator

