From these data, a sample size of 32 will have 81% power to find a statistically significant result for Aim 1 (two tails) assuming the population mean response is the 30% reported by our colleagues in Nottingham. This sample size provides 75% power to detect clinically meaningful (-25%) improvement (one tailed).

Estimating screen failures and dropouts at a total rate of 27%, we will plan to enroll up to 44 participants to arrive at 32 who complete the entire study.

INCLUSION CRITERIA

Inclusion criteria for all subjects:

- Age 15-64 inclusive at initial screening visit
- Informed consent by adult subject; assent by child and informed consent by guardian
- Current DSM-5 Tourette's Disorder or Persistent (Chronic) Tic Disorder
- At least 1 tic per minute (average) during the first 5-min. baseline video session on the first visit (as scored during the session by the investigator)

EXCLUSION CRITERIA

Exclusion criteria for all subjects:

- Unable to complete study procedures for any reason
- Has an implanted device that could be affected by electrical current
- Pregnancy known to participant or (for children) to the parent
- Known or suspected primary genetic syndrome (e.g. Down syndrome, Fragile X)
- Intellectual disability (known, or likely from history and examination)
- Head trauma with loss of consciousness for more than 5 minutes
- Significant neurologic disease, not counting TS (exceptions include febrile seizures or uncomplicated migraine)
- Severe or unstable systemic illness
- Factors (such as exaggerated signs) that in the judgment of the principal investigator make the video recording or YGTSS an inaccurate assessment of tic severity
- Judged by investigator to be unlikely to complete study procedures or to return for later visits
- Change in somatic or psychotherapeutic treatment in the 2 weeks preceding the first stimulation visit
- Planned change in somatic or psychotherapeutic treatment between the 2 stimulation visits

CONCOMITANT MEDICATIONS

Required: none

PROHIBITED MEDICATIONS

none

TREATMENTS AND DOSAGE

Rhythmic

- 10 Hz for 1-minute epochs (to replicate **Current Biology** report)

- 12 Hz for 5-minute epochs

Arrhythmic

- Same number of pulses per minute as in the rhythmic condition, but with a random inter-pulse interval, as implemented by the Nottingham group in the **Current Biology** report

Both

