[Time Frame: up to 20 minutes after the end of stimulation at each study visit up to 1 month]

6. CGI-I, participant

Clinical Global Impression of Improvement (CGI-I), rated by participant. The CGI-I is a 7-point scale ranging from 1 = very much improved to 7 = very much worse.

[Time Frame: 5-25 minutes after the end of stimulation at each study visit up to 1 month]

7. CGI-I, investigator

Clinical Global Impression of Improvement (CGI-I), rated by investigator.

[Time Frame: 5-25 minutes after the end of stimulation at each study visit up to 1 month]

8. VAS rating of premonitory urge severity

Participant rates the maximal severity of any premonitory urges over the preceding minute, from 0=no premonitory urge to 100=maximally uncomfortable premonitory urge, using a Visual Analog Scale.

[Time Frame: Before MNS begins and at the end of each 5-min. MNS on or off block, at each study visit up to 1 month]

9. Rating of therapeutic effect using the CGI Efficacy Index

Participant rates peak improvement experienced during the visit using the 4-point scale of the CGI (Unchanged or worse; Minimal - Slight improvement that doesn't decrease the overall impact of

symptoms*; Moderate - Decided improvement. Partial remission of symptoms; Marked - Vast improvement. Complete or nearly complete remission of all symptoms). * = "Minimal" option anchor text slightly edited from original

[Time Frame: 5-25 minutes after the end of stimulation at each study visit up to 1 month]

10. Rating of discomfort using the CGI Efficacy Index (edited)

Participant rates peak discomfort experienced during the visit using the 4-point scale of the CGI:

"Overall, today, how much DISCOMFORT did the stimulation cause? If discomfort is the wrong word, please substitute any negative effects or side effects of stimulation. (No discomfort; Discomfort noticeable, but not severe enough to concern me or to turn it off; Enough discomfort, impairment of functioning or social embarrassment that I would only keep it on if the benefit was considerable; Caused discomfort, impairment of functioning or social embarrassment to a degree that any treatment benefit was not worth leaving it on).

[Time Frame: 5-25 minutes after the end of stimulation at each study visit up to 1 month]

11. Blindedness assessment

Participants guess whether they received the active or sham MNS condition, and rate their certainty for that guess on a 0-3 scale (0 = pure guess, 3 = certain).

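### No discomfort rating is planned for a visit that stops early, so the tolerability summary can omit the least tolerant participants

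*Combined protocol and SAP*

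**What the plan says.** In the stimulation protocol, eligibility is reviewed and documented at step 8. The first pulses come at step 9, where the current is raised until the thumb twitches. Step 9 notes: "Some subjects may wish to withdraw at this point if suprathreshold stimulation is too uncomfortable". The same sentence adds that participants aged 15 and over in the Nottingham study tolerated the stimulation.

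The on and off blocks follow at step 12 and last 29 to 44 minutes. The debrief is step 15. Item 15a takes "ratings of tic improvement and discomfort using the CGI Efficacy Index", and item 15b is to "ask for comments on benefit, tolerability, side effects".

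Secondary Outcome Measure 10 reads: "Participant rates peak discomfort experienced during the visit using the 4-point scale of the CGI". Its worst category is discomfort or other negative effects "to a degree that any treatment benefit was not worth leaving it on". Its time frame is "5-25 minutes after the end of stimulation at each study visit up to 1 month".

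The Aim 3 paragraph of the data analysis section says only that discomfort will be summarised descriptively. The sample size section plans for 32 completers out of up to 44 enrolled, with a single 27% allowance for screen failures and dropouts together. One exclusion criterion is "Unable to complete study procedures for any reason".

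**The concern.** A person who stops because stimulation is too uncomfortable has shown something close to what the worst category of Outcome 10 describes. The schedule has no point at which that person is asked. If the rating is missing, it is missing because of the quantity being measured, and the summary of those who were rated is tilted towards good tolerability.

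The Objectives section names tolerability with the longer blocks among the preliminary data needed for a future application, and the study is meant to inform a decision on a trial of a wearable device. A discomfort summary that can lose its least favourable observations is weak support for that purpose. What the participant felt on the day is also hard to recover later.

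**Working it through.** **Order of events.**

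| Step | Event | Discomfort data scheduled |
|---|---|---|
| 8 | Eligibility documented | none |
| 9 | First pulses; withdrawal for discomfort foreseen | none |
| 12 | On and off blocks | none |
| 15a, 15b | Debrief | Outcome 10 rating; side-effect question |

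**Is the time frame built around a finished session?** Step 12 ends with one to four 5-minute off blocks, that is 5 to 20 minutes between the last stimulation and the debrief. The Outcome 10 window of 5 to 25 minutes fits that sequence. The block total also checks: 4 × 1 + 4 × 5 = 24 minutes, plus 5 to 20 gives 29 to 44. No other section schedules the rating at an early stop, asks for the reason for stopping, or defines who is counted in the summary.

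**The plan's own figure.** Enrolment for 32 completers at a 27% loss: 32 / (1 − 0.27) = 43.8, rounded up to 44. This reproduces. Non-completers can number up to 44 − 32 = 12, and 12/44 = 27.3%. The split of the 12 by cause is not given.

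**Illustration of the effect.** Let x be the number of the 32 completers who choose the worst category, and k the number who withdraw for discomfort without a rating. Both are assumptions. The summary of rated participants shows x/32. The proportion who either chose the worst category or withdrew for discomfort is (x + k)/(32 + k). Other non-completers are left out of this calculation.

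| x | Shown among rated | k = 2 | k = 4 | k = 6 |
|---|---|---|---|---|
| 0 | 0/32 = 0% | 2/34 = 5.9% | 4/36 = 11.1% | 6/38 = 15.8% |
| 2 | 2/32 = 6.3% | 4/34 = 11.8% | 6/36 = 16.7% | 8/38 = 21.1% |

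A confidence interval would not repair this. The exact two-sided 95% upper limit for 0/32 is 1 − 0.025^(1/32) = 10.9%. It describes sampling error among those rated and says nothing about people left out. With k = 4 the combined figure, 11.1%, already lies just above it.

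**The case against.** The strongest reply is that the documents are silent rather than wrong. They list the steps of a full session and do not say that an early stopper skips the debrief. Outcome 10 asks about the peak during the visit, timed from the end of stimulation, so staff could put it to someone whose stimulation ended early. Any adverse event also goes to the review board whether or not the visit is completed. Step 9 itself cites good tolerability from age 15, the lower age limit here.

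This limits the point. A reader might infer four stronger things that the documents do not support:

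- **That discomfort is reported for completers only.** The restriction to people with both visits is written for the rhythmic versus arrhythmic tic comparison (Outcomes 3 and 4, Aim 2), not for Outcome 10. Someone who finishes the first visit and stops at the second keeps a first-visit rating.
- **That a withdrawal at step 9 becomes a screen failure through the exclusion criterion.** At the first visit, eligibility has already been documented at step 8, and step 9 calls the exit a withdrawal. The broad wording of the exclusion leaves relabelling possible but does not direct it.
- **That intolerant participants are replaced by tolerant ones.** The figure of 44 is a ceiling, and no replacement rule is given.
- **That every discomfort withdrawal belongs in the worst category.** That category weighs discomfort against treatment benefit, which a person leaving at threshold finding has not experienced. Nor has that person received a 5-minute block, the setting in which the Objectives mention tolerability.

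What remains is that collection at an early stop depends on staff initiative, with no rule for recording the reason or counting the result. Adverse event reporting supplies neither the discomfort scale nor a denominator.

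**Conclusion.** The point holds as a gap in planned data collection and reporting. Discomfort is scheduled only at the end of a full session, withdrawal for discomfort is foreseen before that, and nothing says how such a visit is rated or counted. If the plan is followed as listed and early stoppers are not asked, the likely direction of the error is towards better apparent tolerability.

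The size cannot be derived from the documents. The 5.9% and 11.1% figures assume no completer in the worst category and 2 or 4 withdrawals without any rating, as when they stop during the first visit. A reader might take 12/44 = 27.3% as the possible understatement. It is only an outer bound: it requires all 12 non-completers to have stopped for discomfort without a rating, whereas the 12 also include dropouts for other reasons and people screened out before any pulse, for example for too few tics at baseline. No stated figure in the plan is wrong on this point.

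The outcome is secondary and descriptive in a pilot. The change is still worth making, because it is nearly free and removes an error that would favour the device.

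**What to change.** - Give the existing Outcome 10 item and the step 15b question at the moment of any early stop from step 9 on, at either visit, and record the reason for stopping. Amend the Outcome 10 time frame to allow this.
- Beside the Outcome 10 categories, report the number who withdrew for discomfort as a separate line, by visit and by stage (threshold finding or blocks). Use everyone who received any pulse as the denominator.
- State that a withdrawal after step 8 is not counted as a screen failure, and report screen failures and withdrawals separately.
- Do not automatically place a withdrawal in the worst category. The separate line conveys the information without imputing a judgement about benefit.

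The cost is a few lines of protocol text and one short REDCap form at early exit, with no added visit, staff or sample size. The tolerability figure may look less favourable. The change concerns data collection and reporting only, and leaves stimulation and the conditions for stopping as they are.

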You may experience one or more of the risks indicated below from being in this study. In addition to these, there may be other unknown risks, or risks that we did not anticipate, associated with being in this study. You will be told of any new information that may affect your willingness to participate in this study. [name] will answer any questions you have about these risks.

MNS

Likely:

- Discomfort in the forearm, wrist or hand during active stimulation
- Mild skin irritation from applying or removing the surface electrodes

Other study procedures

Likely:

- The questionnaires and interview may be slightly boring, fatiguing or challenging.
- The video recordings may be slightly boring

Rare:

- The questions that you are asked during this study could make you feel uncomfortable. If any question makes you feel uncomfortable, you may choose not to answer it.
- Confidential information about you may be accidentally disclosed. However, we think the risk of accidental disclosure is small. The information we gather during the course of the study is coded only by a study number and is kept separately from your name, address, etc.

LOCATIONS / SITES OF STUDY

Data collection: Washington University in St. Louis

Data analysis: Washington University in St. Louis

STUDY DURATION

Anticipated duration of entire research activity per participant:

- 2-4* days, usually over the course of 1-2 weeks

* Planned participation includes a screening visit followed by two stimulation sessions, the first of which may occur on the same day as the first stimulation session. The maximum of 4 days rather than 3 allows one additional make-up MNS session for each participant in the event of technical problems that prevent completion of the procedures.

Anticipated duration of entire research activity:

One year

SAMPLE SIZE

N = 32 (study completers)

Power considerations

We can estimate variance from the Nottingham tic frequency results. Fig. 5 in ref. [6] shows the SD of the improvement in tic frequency between the MNS on and off conditions to be ~81 (total tics per condition). The mean difference between conditions was ~41, corresponding to a nearly 30% mean decrease in tic frequency. A 25% decrease in tic severity using the YGTSS Total Tic Score (TTS) is highly predictive of *clinically meaningful* clinical improvement [17], and the TTS is highly correlated to tic frequency on video recordings [18,19].

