- Square-wave 200 μ s pulses triggered by computer at the threshold for thumb movement (expected ~2-15mA) to surface electrodes over the median nerve at the right wrist (conductive gel, 30 mm apart center-to-center, anode distal)

ANALYSIS PLAN/APPROACH/METHODOLOGY

Outcome measures

The primary outcome measures are derived from audiovisual recordings (head to elbows), later broken into 1-min. or 5-min. clips, then rated in random order by an experienced movement disorders physician blind to stimulation conditions (on vs. off, rhythmic vs. arrhythmic) and order (rhythmic at first or second visit), who will record tic frequency and rate severity. For the 1-min. MNS on/off blocks, severity is rated on a 5-point scale (from the YGTSS severity item) for each occurrence of any tic, to replicate the methods of the Nottingham group. For the 5-min. blocks, overall tic severity is rated on the same scale once for each 5-min. block. This choice dramatically reduces rater time without sacrificing validity. Analysis for each participant can begin after his/her second stimulation visit is complete and all other data from that participant is checked.

Primary Outcome Measures:

1. Change in tic frequency compared to when MNS is off

An expert rater blind to condition and time point assesses the number of tics per minute. A one-tailed t test will compare mean tic frequency in the last 40 s of on vs. off 1-minute stimulation epochs on the rhythmic MNS day. This analysis replicates that of Study 3 in the Morera Maiquez et al 2020 citation. A secondary analysis will test for carryover effects.

[Time Frame: During rhythmic MNS stimulation]

2. Change in tic severity compared to when MNS is off

Severity is rated on a 5-point scale for each occurrence of any tic. The scale is the Intensity item from the Yale Global Tic Severity Scale [YGTSS], which uses integer scores from 0 (no tics) to 5 (severe intensity). A one-tailed t test will compare mean tic severity in the last 40 s of on vs. off 1-minute stimulation epochs on the rhythmic MNS day. This analysis replicates that of Study 3 in the Morera Maiquez et al 2020 citation. A secondary analysis will test for carryover effects.

[Time Frame: During rhythmic MNS stimulation]

3. Change in tic frequency during rhythmic MNS (vs. arrhythmic MNS)

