An expert rater blind to condition and time point assesses the number of tics per minute. Change in tic frequency from baseline (stimulation off) is compared between 5-minute MNS-on epochs on the rhythmic vs. the arrhythmic day. Subjects who do not complete both stimulation visits will not be included in this analysis. A repeated measures ANOVA will be used to compare effects of visit, order (rhythmic day first or second) and stimulation (on vs. off) on tic frequency. The hypothesized change is a significant interaction of visit, order and stimulation factors ($p \leq 0.05$),

showing greater improvement (off to on) with rhythmic vs. arrhythmic stimulation. This analysis includes the first six 5-minute blocks on each MNS day (i.e., the blocks that all participants complete).

[Time Frame: During rhythmic MNS stimulation]

4. Change in tic severity during rhythmic MNS (vs. arrhythmic MNS)

Overall tic severity for each 5-minute block is rated once on a 5-point scale by an expert blind to condition and time point. The scale is the Intensity item from the Yale Global Tic Severity Scale [YGTSS], which uses integer scores from 0 (no tics) to 5 (severe intensity). For this analysis, we will define tic severity as $\max\{\text{phonic tic intensity score, motor tic intensity score}\}$. Change in tic severity from baseline (stimulation off) is compared between 5-minute MNS-on epochs on the rhythmic vs. the arrhythmic day. Subjects who do not complete both stimulation visits will not be included in this analysis. A repeated measures ANOVA will be used to compare effects of visit, order (rhythmic day first or second) and stimulation (on vs. off) on tic frequency and severity. The hypothesized change is a significant interaction of visit, order and stimulation factors ($p\le.05$), showing greater improvement (off to on) with rhythmic vs. arrhythmic stimulation. This analysis includes the first six 5-minute blocks on each MNS day (i.e., the blocks that all participants complete).

[Time Frame: During rhythmic MNS stimulation]

Secondary Outcome Measures:

5. Change in tic severity after MNS ends

Duration of benefit will be estimated as follows. A repeated measures ANOVA will compare the change in tic frequency from baseline, during each 1-minute-long period following the end of stimulation. Here baseline means the tic frequency during the last 5 minutes of MNS from the same day.

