[Time Frame: 5-25 minutes after the end of stimulation at each study visit up to 1 month]

12. Interest in a portable stimulator

Participants answer the question, "If you had a portable device (about the size of a deck of cards) that delivered stimulation in your daily life like you received either today or at your previous visit, would you expect to use it?"

[Time Frame: Once at the end of the second study visit]

Data analysis

Data storage, sharing and management. Phenotypic data will be collected and stored on REDCap (redcap.wustl.edu). This data will not contain PHI and will be shared on the [Open Science Framework](#). Video recordings will be shared only with explicit optional informed consent.

Overall statistical approach. To prevent "HARKing" (hypothesizing after results are known) [20], we have **registered our hypotheses** and analysis strategy on [OSF.io](#) prior to initiating enrollment. For this pilot study, all statistical tests will be reported independently. Aim 1 and Aim 2 test a small number of hypotheses, and Aim 3 results, which are primarily hypothesis-generating, will be presented with a warning about multiplicity of tests.

Aim 1 (replicating the Nottingham results). The analysis will replicate that of Study 3 in the **Current Biology** report [6], with blinded ratings of tic frequency and severity based on the last 40 s of each 60-s MNS on or off block. A one-tailed t test will compare mean tic frequency in on *vs.* off 1-minute stimulation epochs on the rhythmic MNS day. The analysis will be repeated for tic severity.

Aim 2 (testing whether benefit from rhythmic stimulation exceeds that from the active control, arrhythmic stimulation). Change in tic frequency and severity from baseline are compared between MNS-on epochs on rhythmic *vs.* arrhythmic days. Subjects who do not complete both stimulation visits will not be included in this analysis. A repeated measures ANOVA will be used to compare effects of visit, order (rhythmic day first or second) and stimulation (on *vs.* off) on tic frequency and

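### The 81% power quoted for Aim 1 is for a two-tailed test, but the planned Aim 1 tests are one-tailed; at one-sided 0.05 the frequency test has about 88% (minor, conservative).

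*Combined protocol and SAP*

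**What the plan says.** The Sample Size section sets "N = 32 (study completers") and takes its inputs from the earlier Nottingham study: an SD of the on-off difference of about 81 tics per condition, and "The mean difference between conditions was ~41, corresponding to a nearly 30% mean decrease in tic frequency".

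Two power statements follow, one directly after the other:

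- For the 30% effect: "a sample size of 32 will have 81% power to find a statistically significant result for Aim 1 (two tails").
- For the 25% effect: "This sample size provides 75% power to detect clinically meaningful (-25%) improvement (one tailed").

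The analysis sections are one-tailed throughout for Aim 1:

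- Primary Outcome 1: "A one-tailed t test will compare mean tic frequency in the last 40 s of on vs. off 1-minute stimulation epochs".
- Primary Outcome 2: "A one-tailed t test will compare mean tic severity in the last 40 s of on vs. off 1-minute stimulation epochs".
- Data analysis, Aim 1: "A one-tailed t test will compare mean tic frequency in on" versus off epochs on the rhythmic day, then the same for severity.

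No significance level is printed for these tests. The only level in the document is 0.05, given for the Aim 2 interaction (Primary Outcomes 3 and 4, and Data analysis, Aim 2).

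**The concern.** A power figure should describe the test that will be run. The 81% is labelled two-tailed and the plan has no two-tailed Aim 1 test. The next sentence switches to one tail without comment, so the two figures differ in both effect size and sidedness.

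The practical consequence is how they read together. Moving from a 30% to a 25% reduction seems to cost 6 points (81% to 75%), which makes the design look fairly insensitive to the assumed effect. The plan itself ties 25% to clinical meaningfulness and expects the study to give a go/no-go signal, so this sensitivity is worth showing correctly. The missing Aim 1 alpha adds to the problem: without it, neither figure is fully defined, and nor is a positive Aim 1 result.

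**Working it through.** **Inputs (Sample Size section).** n = 32 completers, each measured on and off; mean difference ≈ 41; SD of the difference ≈ 81. I first take 41 to be the 30% effect, so the 25% effect is 41 × 25/30 = 34.2. Alpha 0.05 is assumed for Aim 1.

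**Method.** Paired t test, df = 31, noncentrality = (mean/SD) × √n. Power = P(T > t_crit), with T noncentral t. The opposite tail of the two-tailed test adds nothing visible. The normal approximation is Φ(noncentrality − z_crit).

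- 30% effect: 41/81 = 0.506; 0.506 × √32 = 2.863.
- 25% effect: 34.2/81 = 0.422; 0.422 × √32 = 2.386.
- Critical t, df 31: 2.040 (two-sided 0.05) and 1.696 (one-sided 0.05).

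**Step 1: the plan's own figures.**

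| Effect | Test | Exact t | Normal | Printed |
|---|---|---|---|---|
| 30% | two-sided 0.05 | 79.2% | Φ(2.863 − 1.960) = 81.7% | 81% |
| 25% | one-sided 0.05 | 75.4% | Φ(2.386 − 1.645) = 77.1% | 75% |

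Both roughly reproduce under their own labels. Solving for alpha gives the same picture: 81% implies a two-sided alpha of 0.057 (exact t) or 0.047 (normal), and 75% implies a one-sided alpha of 0.049 (exact t).

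**Step 2: both effects on each basis (exact t).**

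| Test | 30% effect | 25% effect | Loss |
|---|---|---|---|
| One-sided 0.05 | 87.6% | 75.4% | 12 points |
| Two-sided 0.05, or one-sided 0.025 | 79.2% | 63.7% | 15 points |
| As printed (mixed) | 81% | 75% | 6 points |

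With these inputs no single one-sided alpha gives both printed figures. The one-sided alpha that gives 81% at the 30% effect is about 0.029, and at that level power for the 25% effect is about 66%.

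**Step 3: sensitivity at one-sided 0.05.** The plan calls the decrease of 41 nearly 30%. If 41 stands for r%, the 30% effect is 41 × 30/r and the 25% effect is 41 × 25/r.

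| Reading | 30% effect | 25% effect | Loss |
|---|---|---|---|
| r = 30 (41.0 / 34.2) | 87.6% | 75.4% | 12.1 |
| r = 29 (42.4 / 35.3) | 89.5% | 77.9% | 11.6 |
| r = 28 (43.9 / 36.6) | 91.2% | 80.4% | 10.8 |
| Mean 40.5, SD 81.5 (r = 30) | 86.5% | 74.1% | 12.4 |
| Mean 41.5, SD 80.5 (r = 30) | 88.6% | 76.8% | 11.8 |

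**Step 4: does N = 32 hold?** At one-sided 0.05 with mean 41 and SD 81, power is 80.7% with 26 completers and 82.0% with 27. The planned frequency test therefore reaches the quoted 81% with fewer than 32.

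**The case against.** The best defence is that nothing printed is false. Each power figure carries its own sidedness, each reproduces, and quoting two-tailed power for a test later run with one tail is cautious. The power of the planned test at the more demanding 25% effect is already printed. Only a reader who subtracts two differently labelled figures is misled, and the plan never makes that comparison. All of this stands, and it is why the point is minor.

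A second argument is that 88% depends on an alpha that the plan does not print for Aim 1. At one-sided 0.025 the 30% figure would be 79%, close to the printed 81%. That is true, but the printed 75% would then be wrong, since the test would have about 64%. The 75% fits one-sided 0.05, which makes 0.05 the better inference. It remains an inference; the OSF registration may settle it but is not among the documents.

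Third, the mismatch could be resolved the other way, by making the tests two-tailed. The 81% would then stay and the 25% figure would fall to about 64%. The plan says one-tailed for Aim 1 in all three analysis passages, so restating the power is the smaller change.

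Finally, the inputs are approximate readings from a figure in a 19-patient study. The ranges above cover rounding and the meaning of nearly 30%, not sampling error. The plan also allows a nonparametric analysis if the data are clearly non-normal, and 88% applies only to the t test. These limits apply equally to the printed 81%.

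**Conclusion.** The concern holds, as a minor point in the conservative direction. The 81% is the power of a two-tailed test that the plan does not include. On the plan's inputs, the one-tailed frequency test at 0.05 has about 88% power for a 30% reduction (86.5–88.6% allowing for rounding of the inputs; 88–91% if nearly 30% means 28–30%). For a 25% reduction it has about 75% (74–77% and 75–80% on the same two ranges). The like-for-like loss between the two effects is 11–12 points, not 6.

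This rests on one-sided 0.05, which is assumed, and on the paired t test being used. It covers tic frequency only: the documents give no SD or effect size for the severity test, so Primary Outcome 2 has no power figure on either basis. The sample size is not in question.

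**What to change.** State the significance level and sidedness for Primary Outcomes 1 and 2, and give both power figures for that test. If one-sided 0.05 is intended, the power sentence could read: *With 32 completers and one-sided alpha 0.05, the paired t test on tic frequency has about 88% power for a 30% reduction and about 75% power for a 25% reduction.* If one-sided 0.025 is intended, say so and give about 79% and 64%. If the OSF registration already states the level, copy it from there.

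The cost is one alpha and one power figure, or two power figures under 0.025. The 32 completers, the enrolment ceiling of 44 and the planned one-tailed tests stay as they are.
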